2.5 Correlative Studies Background

Aim 1: *Investigate the expression of PD-L1 and PD-L2 on myeloma plasma cells prior to and at various*

time points after checkpoint blockade and radiotherapy.

Rationale: PD-L1 is highly expressed on plasma cells isolated from patients with multiple myeloma but not on normal plasma cells and PD-L1 is not expressed on plasma cells isolated from patients with monoclonal gammopathy of unknown significance (MGUS)^{3,43-45}. It will be important to confirm and quantify this finding in our study. Additionally, little is known about the expression of PD-L2 on the plasma cells from patients with multiple myeloma, which may affect the immunogenicity of patients with multiple myeloma.

Experimental Design: Expression of these ligands on myeloma plasma cells will be assessed from bone marrow biopsies by immunohistochemistry and flow cytometry staining with anti CD45, CD19, CD38 and CD138 to identify plasma cells, as well as PD-L1 (CD274) and or PD-L2 (CD273). As pre-treatment and serial post-treatment biopsies will be taken, we will compare responses rates to expression levels of PD-L1 and PD-L2 on myeloma cells at various time points.

20 ml bone marrow aspirate and core aspirate will be collected and sent to immunopathology.

Aim 2: Investigate the population of T cells (cytotoxic T cells, helper T cells and regulatory T cells) and their expression of immune checkpoint receptors (PD-1, CTLA-4, LAG3, 2B4, BTLA, TIM3, A2aR) prior to and at various time points after immune checkpoint blockade and radiotherapy.

Rationale: The clinical efficacy of PD-1 blockade is most pronounced in malignancies characterized by the presence of infiltrating effector cells in the tumor bed¹⁹. In contrast, myeloma is characterized by low levels of infiltrating effector cells, so the role of this biomarker in multiple myeloma is unclear. It is also unknown whether bone marrow T cell profiles reflect the T cell profile of the tumor itself in multiple myeloma. Therefore, we will quantify and characterize the T cell population in the site to be irradiated, bone marrow before immune checkpoint blockade and radiotherapy. Additionally, the T cell population will be similarly assayed on serial bone marrow biopsies and compared.

Experimental Design: T cells are broadly categorized into three major groups based on function: cytotoxic T cells, helper T cells (Th), and regulatory T cells (Tregs). Differential expression of markers on the cell surface, as well as their distinct cytokine secretion profiles, allow different subsets to be quantified. For example, CD8+ cytotoxic T cells destroy infected target cells through the release of perforin, granzymes, and granulysin, whereas CD4+ T helper cells have little cytotoxic activity and secrete cytokines that act on other leukocytes such as B cells, macrophages, eosinophils, or neutrophils. Tregs suppress T cell function by several mechanisms including binding to effector T cell subsets and preventing secretion of their cytokines. T cell diversity will be examined by flow cytometry using the following surface marker antibodies/transcription factors along with the expression of immune checkpoint receptors on these cells.

T Cell Subset	Surface Markers/Transcription Factors
Cytotoxic	CD8

Th1	CD4+CXCR3+
Th2	CD4+CCR4+CCR6-
Th9	CD4+CCR4- CCR6+
Th17	CD4+CCR4+CCR6+
Th22	CD4+CCR4+CCR6+CCR10+
NK/T	CD3+CD56+
Tregs	CD4+CD25+FoxP3+

Aim 3: Investigate mutational burden of pre-treatment myeloma samples in the bone marrow and target site utilizing FoundationOne Heme.

Rationale: The efficacy of PD-1 blockade has been correlated with mutational burden and thought to associate with the presence of neoantigens derived from mutational events producing non-self epitopes ¹⁹. In contrast, myeloma is characterized by a modest mutational burden as compared to solid tumors suggesting a more restricted neoantigen profile.

Experimental Design: Genomic profiles of biopsied tumors will be performed using FoundationOne Heme, a comprehensive

platform that applies next-generation sequencing to identify all 4 types of genomic alterations (base substitutions, insertions and deletions, copy number alterations and rearrangements) across all genes known to be drivers of hematologic malignancy. The test sequences the entire coding region of 405 cancer-related genes and employs RNA sequencing across 265 genes to capture a broad range of gene fusions and provides an interpretive report (Figure), including “tumor mutational burden” (TMB), a reproducible estimate of mutation rates across all coding sequences in the genome. Spearman rank correlation will be used to explore the significance of the correlation between TMB and response.

Aim 4: Investigate the T cell receptor (TCR) repertoire in the bone marrow aspirate prior to and at various time points after immune checkpoint blockade and radiotherapy.

Rationale: At the center of the process of the immune system distinguishing self from nonself is

[figure not shown]

Figure: FoundationOne Heme genomic

recognition and binding of a TCR to an antigen displayed in the major histocompatibility complex (MHC) on the surface of an antigen-presenting cell (APC). The naïve TCR repertoire is formed by somatic rearrangements of non-contiguous genes belonging to the variable (*V*), diversity (*D*) and joining (*J*) families (combinatorial diversity). These are adjacent to the constant (*C*) gene in the heterodimeric α - β or γ - δ TCR. Further random insertion and deletion of nucleotides at the rearrangement positions create junctional diversity of the highly variable complementarity-determining region 3 (CDR3 region). The CDR3 region is unique for every T cell clone and encodes the receptor portion that makes the majority of TCR contacts with antigenic peptides bound by the MHC. The frequency of a specific CDR3 sequence indicates the abundance of its T cell clone. Thus, comprehensive TCR sequencing could provide a representative and quantitative repertoire analysis of specific tumor immunity.⁴⁶ In a neighboring research project (PI: [name]), TCR repertoire analysis was used to investigate effects of anti-CTLA-4 and/or radiation therapy treatment on the TCR β repertoire of tumor infiltrating lymphocytes (TILs) in a breast carcinoma mouse model. The 4T1 tumor model is not sensitive to single treatment using anti-CTLA-4 or radiotherapy, but respond well to the combination of both treatments. With TCR repertoire analysis, treatment-specific clusters of TILs were identified and to show that highly abundant clones rarely were unique to only one animal. Additionally, the data suggest the major role of radiotherapy is to increase the frequency of mid-ranked clones whereas anti-CTLA-4 primarily expands the top-ranked clones. However, when used together, radiotherapy and anti-CTLA-4 increased both top- and mid-ranked clones (Rudqvist et al., manuscript in preparation).

Experimental Design: TCR sequencing from bone marrow aspirate will be performed using the immunoSEQ assay provided by Adaptive Biotechnologies (AB). DNA from samples will be sent for sequencing to AB after which one part of the analysis will be performed utilizing AB's analytical platform the ImmunoAnalyzer 3.0. Furthermore, data will be downloaded and processed using various in-house developed tools for TCR repertoire analysis. Since the recombination process of the TCR is a random process with large variation between individuals, [name] (postdoc in Radiation Oncology at Weill Cornell Medicine) has developed a method for calculating a similarity metric between TCR repertoires (preliminary data not shown). With this approach, questions such as when and how a favorable T cell repertoire develops can more easily be assessed.

2.6 Microbiome Correlative studies

2.6.1 To explore associations of ORR with changes in the microbiome.

While immune checkpoint blockade results in remarkably prolonged disease control in a subset of patients^{47,48} modulators of this phenotype are not well understood. Accumulating evidence suggests the gut microbiota play a critical role in response to both anti-PD-L1 efficacy and CTLA-4 blockade: two recently published studies by Vetizou *et al.* and Sivan *et al.* demonstrated in mouse models that the gut microbiome critically impacts response to immunotherapy^{47,48}. Remarkably, by altering the composition of commensal microbiota, the response to CTLA-4 blockade and anti-PD-L1 therapy could be manipulated and therapeutic response markedly enhanced. These pre-clinical studies provide strong rationale for our hypothesis that the human gut microbiome composition will

correlate with response to ICB and RT. Identification of commensal organisms harbored in patients with heightened antitumor immune response can ultimately be manipulated to achieve desired outcomes in a greater proportion of patients. Fecal transplant is an established clinical technique whereby microbiota can be transferred into humans to induce select therapeutic outcomes, providing direct clinical applicability of any findings ⁴⁹.

The study by Vetizou *et al.* underscores the dependence of CTLA-4 blockade on commensal microbiota ⁴⁸. First, the authors demonstrate that anti-CTLA-4 therapy is ineffective in mice that are housed in germ-free cages or treated with antibiotics.

By transferring specific gut microbiota back into antibiotic-treated or germ-free mice, the anticancer efficacy of CTLA-4 blockade could be recovered. The transfer of T cells specific to *Bacteroides fragilis*, or immunization with dendritic cells exposed to *B. fragilis* polysaccharides, also restored the antitumor effect of CTLA-4 blockade. Additionally, Vetizou *et al.* explored human gut microbiome changes in 25 malignant melanoma patients treated with CTLA-4 blockade, who at baseline fell into three microbial cluster patterns (Clusters A-C). During treatment, the microbial composition altered, becoming more similar to cluster pattern "C" and distant from cluster pattern "B". Subsequent fecal transplantation from cluster C patients into mice resulted in a significant response to CTLA-4 blockade, whereas transplantation from cluster B patients had no response, providing evidence that host gut microbial composition has a significant impact on likelihood of ICB success.

Sivan *et al.* likewise provides compelling data supporting the importance of gut microbiota in determining treatment efficacy to ICB ⁴⁷. The authors compared growth of melanoma cell lines in two sets of mice harboring distinct gut microbiota, with differential tumor growth and response to PD-L1 therapy, and identified a specific bacterial species, *Bifidobacterium*, to be associated with antitumor immunity. By transferring *Bifidobacterium* from JAX mice to poorly-responding TAC mice, the authors were able to improve baseline anti-tumor immunity, and significantly enhance anti-PD-L1 therapy response. The therapeutic effect of *Bifidobacterium* was established to arise from altered dendritic cell function and increased priming of tumor-specific CD8+ T cells. Only live bacteria could achieve this effect, implying that augmentation of dendritic cell function requires direct interaction of host cells with gut microbiota ⁴⁹. These novel findings signify that the gut microbiome composition impacts response to anti-PD-L1 therapy and can be manipulated to enhance treatment response, providing impetus for similar analyses in human subjects.

Taken together, the above preclinical studies lend strong support towards collection of gut microbiome samples from patients enrolling on all future immunotherapy studies. We propose to collect stool samples from study patients before treatment and at day 21, 3 months and 6 months for analysis of microbiome composition and changes after ICB and RT. Both pre-clinical and clinical data demonstrate that the addition of RT to ICB creates a robust immune response, eliciting anti-tumor immune responses in otherwise non-responding patients. Given that we expect a similar heightened response in our proposed study, our patient cohort with its expected dichotomous outcomes will be particularly suitable for microbiome analysis. The results will be an important step towards understanding, and ultimately harnessing, the interplay between the human gut microbiome and anti-tumor immune response.

Methods Stool collection will occur before treatment, at day 21, at 3 months and 6 months to

explore changes of the microbiome during ICB. Bacterial diversity and taxonomy will be estimated by high throughput sequencing (HTS) of 16S rRNA amplicons, using the MiSeq platform in the Genomic Technology Core Lab. Methods have been established in the Blaser Lab and proven to yield accurate and reproducible results.^{50,51} Analysis will be based on the QIIME (Quantitative Insights into Microbial Ecology) software package developed by the Knight lab,⁵² and machine learning analyses developed by NYU Center for Health informatics and Bioinformatics (CHIBI) investigators working on NYU Human Microbiome Program studies.^{53,54} Appendix 2 describes the protocol for stool collection.

3 Subject Selection

3.1 Study Population

Patients with a diagnosis of multiple myeloma who meet the inclusion and exclusion criteria will be eligible for participation in this study.

3.2 Inclusion Criteria

1. Subject is, in the investigator's opinion, willing and able to comply with the protocol requirements.
2. Subject has given voluntary written informed consent before performance of any study-related procedure not part of normal medical care, with the understanding that consent may be withdrawn by the subject at any time without prejudice to their future medical care.
3. Must have received 2 consecutive cycles of systemic myeloma therapy.
4. Documented refractory or relapsed and refractory (R/R) multiple myeloma
 - a. patients had less than minimal response, or had achieved at least a minimal response to previous treatment, but progressed within 6 months
 - b. patients who have failed treatment with, are intolerant to, or are not candidates for all available therapies known to be active for treatment of relapsed or refractory myeloma
 - c. patients must have failed, be intolerant or are ineligible to treatment with at least 3 lines of therapy, including an IMiD, proteasome inhibitor and anti-CD38 agent
5. Targetable plasmacytoma, either intra-or extramedullary that is visualized on imaging (PET/CT or MRI) and is causing symptoms (eg. pain, neurological compromise) or potential to cause symptom as per clinician's judgement; and measurable disease at screening, defined as one or more of the following:
 - a. Serum IgG, IgA, or IgM M-protein ≥ 0.5 g/dL
 - b. Urine M-Protein ≥ 200 mg excreted in a 24-hour collection sample
 - c. Involved serum free light chain (sFLC) > 100 mg/L provided the FLC ratio is abnormal
6. Males and Females at least 18 years or legal age of consent per local regulations.
7. Women of childbearing potential (WOCBP) must have two negative serum or urine pregnancy tests (minimum sensitivity 25 mIU/mL or equivalent units of HCG). One 10-14 days prior to start of the study drug and one within 24 hours prior to the start of study drug.
8. Investigators shall counsel WOCBP and male subjects who are sexually active with WOCBP on the importance of pregnancy prevention and the implications of an unexpected pregnancy. Investigators shall advise WOCBP and male subjects who are sexually active with WOCBP on the use of highly effective methods of contraception. Highly effective methods of contraception have a failure rate of < 1% when used consistently and correctly.
9. No condition which would cause unacceptable risk.

3.3 Exclusion Criteria

1. Subjects with solitary bone or extramedullary plasmacytoma as the only evidence of plasma cell dyscrasia.
2. Subjects with monoclonal gammopathy of undetermined significance (MGUS), smoldering multiple myeloma (SMM), Waldenstrom's macroglobulinemia, or POEMS syndrome (plasma cell dyscrasia with poly neuropathy, organomegaly, endocrinopathy, monoclonal protein, and skin changes).
3. Subjects with active plasma cell leukemia (defined as either 20% of peripheral blood white blood cell count comprised of plasma/CD138+ cells or an absolute plasma cell count of 2 x 10⁹/L).
4. Subjects within 100 days of stem cell transplantation.
5. Subjects within 4 weeks of surgery, unless cleared by surgeon.
6. Women who are of childbearing potential not complying to the above described contraceptive measures or are breastfeeding, and sexually active fertile men whose partners are WOCBP if they are not complying to the above described contraceptive measures.
7. Any uncontrolled or severe cardiovascular or pulmonary disease determined by the investigator, including:
 - a. NYHA functional classification III or IV, congestive heart failure, unstable or poorly controlled angina, uncontrolled hypertension, arrhythmia, or myocardial infarction in the past 12 months
 - b. Subjects with interstitial lung disease that is symptomatic or may interfere with the detection or management of suspected drug-related pulmonary toxicity
8. Active infection or know HBV/HCV/HIV.
9. Subjects with an active, known or suspected autoimmune disease. Subjects with type I diabetes mellitus, hypothyroidism only requiring hormone replacement, skin disorders (such as vitiligo, psoriasis, or alopecia) not requiring systemic treatment, or conditions not expected to recur in the absence of an external trigger are permitted to enroll.
10. Subjects with a condition requiring systemic treatment with either corticosteroids (> 10 mg daily prednisone equivalent) or other immunosuppressive medications within 14 days of initiation of study drug. Inhaled or topical steroids, and adrenal replacement steroid doses > 10 mg daily prednisone equivalent, are permitted in the absence of active autoimmune disease.
11. Previous radiotherapy to the area of the target area.
12. Prior exposure to immune checkpoint inhibitor.
13. Persistent toxicities of \geq Grade 1 from prior treatment (including chemotherapy, targeted therapy, experimental agents, radiation, or surgery).

4 Registration Procedures

4.1 Patient Registration

Patients will be centrally registered with the Office of Billing Compliance. To register a patient, submit the following documents via the JIRA Registration Process:

- Legible copy of the HRBAF
- First and last page of signed informed consent form

Registration must be completed within 24 hours of the signing of informed consent.

5 Study Calendar

5.1 Schedule of Assessment

Procedure	Screening (Day 0)	C1D1 (±3 days)	C1D15 (±3 days)	Cycles 2-4		Cycles 5+	Cycles 5+	End of Study
				D1	D15	D1	D15	
Informed Consent	X							
Medical History	X	X		X		X	X	X
Physical Exam	X	X		X		X	X	X
Vital Signs + weight	X	X	X	X	X	X	X	X
Performance Status (ECOG)	X	X		X		X	X	X
Concomitant Medications	X	X	X	X	X	X	X	X
Second Primary Malignancy	X	X	X	X	X	X	X	X
Adverse Events Assessment	X	X	X	X	X	X	X	X
Bone Marrow Aspiration/Biopsy ^a	X ^a			X ^a		X ^a		X ^a
Biopsy of Targeted Lesion	X							
Radiologic bone imaging:								
PET/CT, MRI	X				X			X
CBC w/ plts & diff	X	X	X	X	X	X	X	X
CMP, Mg, Uric Acid, LDH	X	X	X	X	X	X	X	X
Serum or urine pregnancy test	X	X	X	X	X	X	X	X
TSH	X			X		X		
Beta 2 microglobulin	X			X				
Response Assessment								
Serum quantitative immunoglobulins	X	X		X		X		X
free light chains, SPEP & SIFE	X	X		X		X		X
24-Hour urine for urine total protein	X	X		X		X		X
UPEP & UIFE	X	X		X		X		X
TREATMENT								
Nivolumab Infusion ^c		X ^c	X ^c	X ^c	X ^c	X ^c	X ^c	
Radiation to Targeted Lesion ^b		X ^b						
RESEARCH PROCEDURES								
Stool Samples (before nivo infusion) ^d		X ^d			X ^d	X ^d		
Saliva Sample collection (before nivo)		X						

Foot notes:

- a. Bone marrow aspirate pre-nivolumab infusion on C2D1, C4D1, C7D1, C10D1 and Q 12 weeks thereafter and as needed to confirm CR
- b. One course of radiation (6GY x 5 fractions), with first radiation on D1 AFTER IV nivolumab
- c. All Infusions will have a ± 3 day window.
- d. Stool samples will be collected on Day1, end of Radiation, C4D1 and C7D1.

5.1.1 Screening Visit – (Day 0 - day28)

After proper documentation of the informed consent process, patients will undergo screening procedures which will include standard of care labs, specified laboratory values as defined by International Myeloma Working Group (IMWG) Criteria, PET/CT –MRI, baseline imaging, bone marrow aspiration biopsy, and target lesion biopsy as outlined in section 5.1 schedule of assessments.

5.1.2 Treatment Phase

Once eligible, patients will receive immunotherapy, nivolumab, intravenously at 240 mg every two weeks. Infusions will be given over 30 minutes (not bolus or IV push). Patients will also receive radiation of 6 Gy x 5 fractions the first week of starting immunotherapy. Immunotherapy treatment starts with the first radiotherapy fraction. Nivolumab will be given every 2 weeks. Patients will have specified laboratory values measured monthly and evaluated for response as defined by International Myeloma Working Group Criteria. Patients will continue to receive their respective immunotherapy for up to three years or until disease progression or dose limiting toxicity is reached. Patients will remain on therapy for up to 6 cycles in the setting of stable disease and for up to a year in the setting of a PR or better by 6 cycles.

5.2 Response Assessment at Week 12

Patients will have specified laboratory values measured monthly and evaluated for response as defined by International Myeloma Working Group Criteria. Patients without progression of disease as defined by IMWG criteria including assessment of plasmacytoma(s) by PET/CT will continue to receive nivolumab every 2 weeks.

5.3 Duration of Therapy and Criteria for Removal from Study:

In the absence of treatment delays due to adverse event(s), treatment may continue until one of the following criteria applies:

1. Progression of disease as defined by IMWG criteria,
2. Intercurrent illness that prevents further administration of treatment,
3. Unacceptable adverse event(s),
4. Patient decides to withdraw from the study, or
5. General or specific changes in the patient's condition render the patient unacceptable for further treatment in the judgment of the investigator.

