1. Changing personnel : Replacing Research Nurse [name] with [name]
2. Changing personnel: Data Manager (Myeloma team): [name]
3. Section 3.3 - Exclusion criteria #12 - Prior exposure to immune checkpoint inhibitor
4. Correcting Nivolumab infusion from 60 mintues to 30 minutes as per BMS and FDA treatment prescriptions.
5. Clarifying stool collection timepoints : Baseline, end of radiation, C4D1 and C7D1
6. saliva collection added to the calendar for C1D1 (before infusion)
7. Adding investigator : [name]
8. Updated Appendix 2 : for stool collection timepoints.
9. Clarifying radiation given as 5 fractions and removing “consecutive days” language.
10. Removing immune monitoring blood samples from section 8.1, 14.2 and 14.5.
11. Revising bone marrow aspiration to 20ml.

Informed consent changes :

1. Clarifying that patients will receive 5 fractions of radiation treatment.

Protocol Summary

Full Title:	Radiotherapy and Immunotherapy for Systemic Effect in Myeloma (RISE-M) Trial
Short Title:	RISE-M Trial
Clinical Phase:	II
Principal Investigator:	[name], MD
Sample Size:	N = 30
Accrual Ceiling:	This study will enroll 30 subjects and screen up to 50.
Study Population:	Eligible patients will have multiple myeloma.
Accrual Period:	2 years
Study Design:	Eligible patients have multiple myeloma with measurable disease in the blood and a targetable soft tissue or bony lesion with radiotherapy. All eligible patients will receive immunotherapy (Nivolumab) plus radiotherapy, 6 Gy x 5 fractions, to a targetable lesion. Immunotherapy treatment starts with the first radiotherapy fraction. Nivolumab will be given every 2 weeks. Patients will have specified laboratory values measured bi-monthly and evaluated for response at 12 weeks as defined by International Myeloma Working Group Criteria. Patients will continue to receive their respective immunotherapy until disease progression or dose limiting toxicity is reached.
Study Duration:	Patients will have approximately 25-30 visits and a follow up for up to 3 years.
Study Agent/Intervention:	Patients with multiple myeloma will receive Nivolumab intravenously at 240 mg every two weeks. Infusions will be given over 30 minutes (not bolus or IV push). Patients will continue to receive infusions every two weeks until disease progression or dose limiting toxicity is reached. Patients will receive 5 fractions of radiation. A dose of 6 Gy x 5 days will be administered.

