7.3 Preparation and Administration of Nivolumab

Dose Calculations

For Multiple myeloma: Nivolumab is given every 2 weeks. The recommended dose of nivolumab is a flat dose of 240mg administered as an intravenous infusion over 30 minutes every 2 weeks until disease progression or unacceptable toxicity.

Visually inspect drug product solution for particulate matter and discoloration prior to administration. Nivolumab is a clear to opalescent, colorless to pale-yellow solution. Discard the vial if the solution is cloudy, discolored, or contains extraneous particulate matter other than a few translucent-to-white, proteinaceous particles. Do not shake the vial.

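### Nivolumab duration is stated in conflicting ways (6 cycles or one year by response, three years, no maximum), and the patient-level toxicity stop lacks one term and a usable definition

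*Combined protocol and SAP*

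**What the plan says.** On duration:

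- Summary, Study Agent/Intervention: "Patients will continue to receive infusions every two weeks until disease progression or dose limiting toxicity is reached". The Study Design entry says the same in similar words.
- 5.1.2: "Patients will continue to receive their respective immunotherapy for up to three years or until disease progression or dose limiting toxicity is reached".
- 5.1.2, next sentence: "Patients will remain on therapy for up to 6 cycles in the setting of stable disease and for up to a year", where the year applies to patients with PR or better by 6 cycles.
- 5.2, under a week-12 heading: "Patients without progression of disease as defined by IMWG criteria including assessment of plasmacytoma(s) by PET/CT will continue to receive nivolumab every 2 weeks".
- 5.3: "treatment may continue until one of the following criteria applies". Five criteria follow (progression, intercurrent illness, unacceptable adverse events, withdrawal, change in the patient's condition). None is a maximum duration.
- 7.3: dosing "every 2 weeks until disease progression or unacceptable toxicity".

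On the toxicity stop:

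- The Summary and 5.1.2 use dose limiting toxicity (DLT), 5.3 uses unacceptable adverse events, and 7.3 and 12.3 use unacceptable toxicity.
- Section 11.3.5 defines a DLT as a grade 4 non-hematological toxicity, a toxicity that interrupts treatment for more than 6 weeks, a treatment-related death, or a treatment-related grade 3 non-hematological toxicity. It uses the definition for a Bayesian rule that pauses the study for review.
- Table 1 in 7.4 sets out, reaction by reaction, when nivolumab is withheld and when it is permanently discontinued.
- Section 12.3 states that unacceptable toxicity is defined in Section 15.

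**The concern.** These are operative rules for stopping an investigational agent. Two investigators who both follow the protocol could treat patients in the same state for different lengths of time. That changes exposure and the regimen that the PFS and OS estimates describe. It also changes safety follow-up: 12.2 ties SAE collection partly to discontinuation of dosing, and 11.3.5 gives no end to DLT observation, so longer treatment means longer time at risk under the pause rule.

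On toxicity, an investigator who reads in the Summary or 5.1.2 that treatment ends at DLT is not told where to find the meaning of that term. The one definition in the document may send the patient off treatment where Table 1 would allow treatment to resume.

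**Working it through.** The plan gives no total-exposure figure to reproduce. The check is a comparison of the passages, with infusion counts to give the scale.

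**Cycle length (inferred; the documents do not state it).** The calendar has D1 and D15 columns and dosing is every 2 weeks, so 2 × 14 = 28 days. Footnote a times marrow samples "pre-nivolumab infusion on C2D1, C4D1, C7D1, C10D1 and Q 12 weeks thereafter". C4, C7 and C10 are three cycles apart, and 12 weeks / 3 = 4 weeks, which agrees.

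**Infusions**, with infusion k on day 1 + (k − 1) × 14 and each limit counted from the first dose (an assumption):

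| Limit | Days | Infusions | Last infusion |
|---|---|---|---|
| 6 cycles | 6 × 28 = 168 | 168/14 = 12 | 1 + 11 × 14 = day 155 |
| One year | 364 | 364/14 = 26 | 1 + 25 × 14 = day 351 |
| Three years | 1,092 | 1,092/14 = 78 | 1 + 77 × 14 = day 1,079 |
| No maximum | – | unbounded | – |

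With 365 and 1,095 days, one more infusion fits in each (days 365 and 1,093), giving 27 and 79.

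**Where the rules part.** C7D1 is day 1 + 6 × 28 = 169. Section 11 sets the response evaluation at 84 ± 7 days, so at the latest day 84 + 7 = 91. The duration conflict begins after the primary endpoint has been read.

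**Patient on day 169 with no progression and no toxicity stop:**

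| Status | 5.1.2, response sentence | 5.1.2, preceding sentence | Summary, 5.2, 5.3, 7.3 |
|---|---|---|---|
| Stable disease | stops (12 infusions) | may go on to three years | continues or may continue, no maximum |
| Minimal response | not addressed | may go on to three years | same |
| PR or better by 6 cycles | up to one year (about 26) | may go on to three years | same |

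Section 9.1 defines stable disease as excluding minimal response, so the stable-disease limit does not cover minimal response by definition.

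**Visit count.** The Summary expects approximately 25–30 visits. One year gives 26 infusions + screening + end of study = 28, before any radiation-only attendances. Six cycles gives 12 + 2 = 14, and three years gives 78 + 2 = 80. The figure fits about one year.

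**Toxicity: two possible readings.**

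- If 11.3.5 governs the patient-level stop, every treatment-related grade 3 non-hematological toxicity ends treatment. Table 1 instead withholds, and footnote a allows resumption at grade 0 or 1, after grade 3 hypophysitis, grade 3 hyperglycemia, grade 3 rash and the first occurrence of another grade 3 reaction. The two then conflict.
- If 11.3.5 governs only the pause, a patient can count toward the pause and still resume under Table 1. There is then no conflict with Table 1, but the DLT stop in the Summary and 5.1.2 has no definition stated to apply to it.

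**Pointer.** Section 15 is Appendix 2, the instructions for collecting stool at home. It defines no toxicity.

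**The case against.** The best defence is that the response-specific sentence in 5.1.2 qualifies the general wording, with three years as an outer ceiling. The uncapped passages are also unequal: 5.2 sits under a week-12 heading, before either limit applies; 5.3 is permissive; 7.3 is recommended-dose wording under a dose-calculation heading. The 25–30 visits suggest that about a year was intended.

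Part of this stands. The visit count makes 78 infusions or unlimited treatment extremes of the text rather than expected exposure. But no passage says that the specific sentence prevails. Section 5.3, which carries duration of therapy in its title, lists no time limit, and the Summary omits one twice. As a ceiling, three years could be reached by neither group that 5.1.2 limits. The visit count does not settle the stable-disease limit.

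On toxicity, it is fair to say that 7.4 is the detailed patient-level rule and that 11.3.5 speaks only of pausing the study. The conflict with Table 1 is therefore conditional.

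Some stronger readings are tempting but unsupported:

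- A reader might infer that DLT has no patient-level definition. Section 11.3.5 does define it by events in a patient; what is missing is a statement that it applies to the patient-level stop.
- A reader might infer that the grade 4 rules match. Section 11.3.5 covers only non-hematological grade 4 events, while Table 1 discontinues for any life-threatening or grade 4 reaction.
- A reader might infer that the calendar contradicts the 6-cycle limit because it schedules pre-infusion samples at C7D1 and later. Those samples can be read as applying while infusions continue.
- A reader might count 6.3 as another conflicting stop. It sets a condition for starting the next dose, under a heading on radiation adverse events.

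**Conclusion.** The duration conflict is in the text and needs correction. For stable disease the limit is 12 infusions under one sentence, up to about 78 under the sentence before it, and unstated elsewhere. Minimal response has no response-specific rule. The counts assume 28-day cycles, no missed doses and limits counted from the first dose; the contradiction itself does not depend on them.

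Because the rules part only at day 169, the documents do not support an inference that this conflict disturbs the 12-week response rate or the two-stage decision. It bears on exposure, safety follow-up and the interpretation of PFS and OS.

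On toxicity, the plan uses three terms for one decision, gives no cross-reference from the DLT stop to 11.3.5, and would conflict with Table 1 if that definition governs individual patients. Confidence is high for the duration conflict and the wrong Section 15 pointer. The conflict with Table 1 depends on a reading that the documents leave open.

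**What to change.** The investigators must:

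1. Reconcile the Summary, 5.1.2, 5.2, 5.3 and 7.3 to one duration rule that covers stable disease, minimal response and PR or better.
2. State whether the DLT definition in 11.3.5 applies to individual patients, to the study-level pause, or to both, and reconcile it with 7.4 accordingly.
3. Use one term for the patient-level toxicity stop throughout.
4. Correct the Section 15 pointer in 12.3.

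No view is given on which duration or stopping rule is right. The cost is amendment wording; the sample size and the two-stage rule do not change.
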